5.4 Study Rationale and Purpose

Inhalation therapy is the cornerstone therapy in asthma and COPD patients. Unfortunately, many errors are associated with the use of inhalers, which leads to poor outcome for patients. Problems with the use of pressurized metered dose inhalers were described shortly after the launch of pMDI and still persist today. The use of dry powder inhalers (DPI's) is also frequently associated with errors.

The most common errors in the use of pMDI's are incorrect coordination, insufficient depth and/or speed of inspiration and no postinhalation breath-hold in.

The most frequent DPI errors are no complete expiration before inhalation, incorrect preparation and lack of postinhalation breath-hold in.

The overall prevalence of poor technique was 31%, of acceptable technique 41% and of correct technique only 31%. It can be concluded that incorrect inhaler technique in asthma and COPD patients is unacceptably frequent. Over the past 40 years, the prevalence of correct inhaler technique has not improved. The lack of correct inhalation technique may be a major obstacle, which withholds patients from achieving optimal asthma or COPD control. (7)

Incorrect use of inhalers is associated with reduced disease control. The strongest associations have been found between incorrect inhaler technique and older age, lower schooling and lack of

instruction about the correct inhaler technique by healthcare workers. These associations are independently of the inhaler type. Poor inhaler use is most common in older ages, but can occur at all ages. The misuse of inhalers is associated with an elevated risk of hospitalization, visits to the emergency department, treatments with oral corticosteroids and antimicrobials, and poor disease control. Instruction by healthcare workers about the correct use of inhalers is the only modifiable factor that can be useful to reduce the prevalence of inhaler misuse. (8)

The choice of inhalation device is an important decision and is often as important as the medication put in the device to achieve optimal outcomes for patients with asthma or COPD. The optimization of treatment could be established by switching between devices instead of increasing or changing the pharmacological therapy. There are multiple differences between the various devices such as particle size, release mechanism, drug deposition and required inspiratory flow. Switching devices should never be done without the patient consent. A patient should feel comfortable with their device in order to use it properly, which makes that switching of device is a careful process in which the patient has to be involved. (9)

In conclusion, the purpose of the study is to identify patient/inhalation mismatch by using objective measurements.

5.5 Rationale for Study Design

All assessments can be made on the spot following the consultation, which allows a cross sectional design.

5.6 Rationale for Dose and Regimen/Schedule Selection NA

6 Study Schematic and Schedule of Activities

6.1 Study Schematic

Characteristics of the study	
Informed consent procedure:	
 ▪ Available in Dutch and French ▪ Signature and date written by participant
Inclusion criteria:	
 ▪ COPD patients (GOLD II-IV) ▪ Patients with severe asthma ▪ Patients with asthma aged ≥ 70y ▪ Patients with mild-to moderate asthma aged < 70y
Exclusion criteria:	
 ▪ Patients with asthma or COPD not on inhaled therapy for maintenance treatment ▪ Patients younger than 18y ▪ Patients unable to give their informed consent due to mental or physical disability ▪ Patients who don't speak French or Dutch
Collection of data form patient file:	
 ▪ Choice of inhaler by physician (current inhaled maintenance treatment) ▪ GOLD grade and group (COPD patients) ▪ GINA treatment step (asthma patients) ▪ Smoking status ▪ Height ▪ Weight ▪ Age ▪ FEV₁, FVC, PIF if available ▪ Oral corticosteroid maintenance dose
Study assessments:	
 ▪ Voluntary deep inhalation ▪ Peak inspiratory flows (PIF's) ▪ Coordination (through a placebo pMDI)
Reporting to treating physician in case of patient/device mismatch	
 ▪ To avoid prescription of inappropriate inhaler

6.2 Study Activities

The study will take place in the respiratory outpatient clinic. Patients will be invited to participate in the study after the consultation with the pulmonologist. All pulmonologists have a flowchart regarding the optimal choice of inhaler at their disposition.

Patients will be provided sufficient time to read the informed consent file and to ask questions about the study. After giving their informed consent they will be screened for eligibility by an

investigator. Demographic data and characteristics will be retrieved from the medical record (EMD) of study participants.

The intervention will consist of three different steps.

First, the patient will perform a deep voluntary inspiration. The patient's ability to perform this inspiration will be assessed and scored by the investigator.

Secondly, the peak inspiratory flows (PIF) will be measured with an In-check Dial device over 5 different resistances.

The minimal and optimal peak inspiratory flow rates (PIFRs) differ by device. A minimum flow of 30 L/min is required for most DPI's. The optimal flow varies from 30 L/min to 35, 45, 50, 60 or 65 L/min. (10)

Due to the fact that there is still discussion about the effectiveness of PIF's going from 30 to 60 L/min, an arbitrary cut-off value will be set at 45 L/min. This cut-off value for sufficient PIF will be measured over a moderate resistance to distinguish subtherapeutic from therapeutic levels. (11) If the patient reaches a PIF lower than 45 L/min, the patient will be asked to make a second attempt.

Subsequently, the patient will receive education about the correct coordination, which is necessary in the use of dose inhalers. The patient will be evaluated for sufficient actuation-inhalation coordination, through a placebo pMDI.

The evaluation of the voluntary deep inspiration, PIF and coordination will be by pass or fail evaluation. Subsequently, the fitness of a patient to use any of the three inhaler classes will be determined by using a diagram designed by a Belgian expert group (unpublished to date; courtesy of [name], ULiège).

If a mismatch between prescribed inhaler and suitable inhaler types is found, the treating physician of the patient will be informed. By doing so, we wish to avoid patients receiving prescriptions for inhalers that they cannot use properly.

7 Study Objectives and Endpoints

7.1 Primary Objective

To study the prevalence of patient/device mismatch based on objective assessments.

7.2 Secondary Objectives

To assess the proportion of patient/device mismatch per patient subgroup.

To assess the fail rates for each objective measurement separately for the entire study population and per patient group.

To correlate the fail rates for each objective measurement separately with patient's characteristics per patient subgroup and overall (age, sex, height, weight, FEV₁, FVC, PIF, GOLD grade and group, smoking status, GINA treatment step, oral corticosteroid dose).

To correlate fail rates for each objective measurement with patient's characteristics.

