Endpoints:	To assess if the choice of inhaler device category differs when based on objective assessments, as compared to the choice made by the treating physician (during routine clinical practice), which is primarily based on subjective evaluation.
Study population:	Asthma and COPD patients treated with inhaled medications. Subjects will be recruited in the respiratory outpatient clinic in UZ Brussel after a scheduled consultation with their pulmonologist.
Number of patients:	40 COPD patients (GOLD II-IV); 20 patients with severe asthma, 40 patients with asthma aged ≥ 70 y, 40 patients with mild-to moderate asthma aged < 70 y
Overview of study design:	Single center, single visit cross-sectional interventional study without device or investigational product
Statistical Considerations:	Descriptive analysis will be used to describe the prevalence patient/device mismatch. Multiple regression analysis will be performed to identify patient characteristics associated with inability to use the 3 main classes of inhalation devices respectively. Due to the exploratory nature of this study, no formal power calculation can be performed.
Sponsor:	This study is an academic study and has no sponsor.
Inclusion Criteria:	
 - COPD patients (GOLD II-IV) - Patients with severe asthma - Patients with asthma aged ≥ 70y - Patients with mild-to moderate asthma aged < 70y
Exclusion Criteria:	
 - Patients with asthma or COPD not on inhaled therapy for maintenance treatment - Patients younger than 18y - Patients unable to give their informed consent due to mental or physical disability - Patients who don't speak Dutch or French
Target Date of first enrolment:	To be determined. Probably Q4 2021.

Target sample size:	No target sample size calculation could be performed due to exploratory nature of the study (please see above)
---------------------	--

2 Protocol Version History

Version No.	Release Date	Summary of Changes

3 Sponsor/Coordinating Investigator Information

Coordinating Investigator (promotor): [name]. [name]

Sponsor: NA

Principal Investigator [name]

Co-investigators: [name]. [name], [name] (co-promotor), [name], [name]

Additional co-researchers: NA

Statistician

Laboratory (ies): NA

Pharmacy: NA

Study Coordinator: [name]

Study sites and co-investigators: respiratory outpatient clinic UZ Brussel

4 List of Abbreviations

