9.2 Inclusion Criteria

- COPD patients (GOLD II-IV)
- Patients with severe asthma included in the Belgian Severe Asthma registry aged <70
- Patients with asthma of any severity aged ≥ 70 y
- Patients with mild-to moderate asthma aged < 70y

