14.4 Statistical Considerations and Data Analysis

The promotor and investigators from UZ Brussel's respiratory division will perform the statistical analysis, with the help of VUB statistician [name].

The statistical plan was discussed during a meeting with professor [name] (see below).

Sample size calculation

This is a purely explorative study, since there is no a priori hypothesis to be confirmed. Hence, no formal sample size calculation is possible.

The findings of this study could later on be confirmed and assessed more extensively in larger dedicated studies.

For this study however, it is important that the patient groups be stratified according to their occurrence in society. We believe this will be the case when the in-and exclusion criteria for this study will be applied.

Statistical analysis

Descriptive statistics will be used to describe the prevalence of patient/device mismatch for the entire study population.

The comparison of the prevalence of patient/device mismatch between patient subgroups and the comparison of the fail rates for each objective measurement separately between patient subgroups will be done by means of the Chi-square test and will be visualized in cross-tables.

To study correlations between patient characteristics (independent variables) and pass or fail rates for each of the three test criteria (dependent variables), box-plots will be used for continuous variables (for example weight and length), whereas the Chi-square test will be used for categorical variables (for example diagnosis, age expressed in years, GOLD stage and GOLD group).

15 Ethical Considerations

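### The overall correlations between fail rates and patient characteristics pool four quota groups without any stratification or adjustment for group, so they may reflect group membership and quota mix

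*Protocol*

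**What the plan says.** The third secondary objective in section 7.2 asks that the fail rate of each test be correlated with patient "characteristics per patient subgroup and overall". Its list of characteristics covers age, sex, height, weight, FEV1, FVC, PIF, GOLD grade and group, smoking status, GINA treatment step and oral corticosteroid dose.

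The synopsis (section 1) sets the group sizes: "40 COPD patients (GOLD II-IV); 20 patients with severe asthma, 40 patients with asthma aged" 70 or over, and "40 patients with mild-to moderate asthma aged" under 70. Section 9.2 makes the asthma groups disjoint by age and severity: "Patients with severe asthma included in the Belgian Severe Asthma registry aged <70", then "Patients with asthma of any severity aged" 70 or over, then mild-to-moderate asthma under 70.

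Section 14.4 gives the only analysis written for these correlations. It opens "To study correlations between patient characteristics (independent variables) and pass or fail rates for each of the three test criteria (dependent variables") and continues that "box-plots will be used for continuous variables", with the Chi-square test for categorical ones. Diagnosis and age appear there as further single variables. Patient group is used only when fail rates and mismatch are compared between subgroups.

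The synopsis also names a multiple regression. Its outcome is inability to use each of the three device classes, it lists no covariates, and 14.4 does not mention it.

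**The concern.** The groups were chosen to differ. Diagnosis separates COPD from asthma, age 70 separates one asthma group from the other two, and severity separates those two from each other. FEV1 and smoking are not group criteria, but they can be expected to differ between COPD and asthma.

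Suppose the groups also differ in how often patients fail a test. The protocol allows for this: it plans to compare fail rates between groups, and section 5.4 cites older age among the strongest correlates of poor technique. A pooled cross-table of fail rate by smoking, or a pooled box-plot of FEV1 by pass or fail, then mixes two things: how the characteristic relates to failure among comparable patients, and how the groups differ. The second part depends on how many patients each quota admits.

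At stake is a secondary objective, namely which patient characteristics go with failing a test. A pooled association could point to a characteristic that separates no one within any group. The primary objective, the prevalence of mismatch, is not touched by this point.

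**Working it through.** The protocol gives no alpha, power, fail rate or distribution of characteristics, so there is no planned figure to reproduce. The check asks how large a pooled association can become when the association inside every group is exactly zero.

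**Inputs from the protocol.** Group sizes are 40 COPD, 20 severe asthma under 70, 40 asthma 70 or over and 40 mild-to-moderate asthma under 70. The sum is 140. The pooled test for a categorical variable is the Chi-square.

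**Assumed inputs.** These are a two-sided 0.05 level, the fail rates and the prevalence of ever-smoking. All values below are in the group order just given.

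**One scenario by hand.** Fail rates are 35/15/35/10% and smokers 90/30/40/30%.
- Smokers: 36 + 6 + 16 + 12 = 70. Expected failures: 36×0.35 + 6×0.15 + 16×0.35 + 12×0.10 = 12.6 + 0.9 + 5.6 + 1.2 = 20.3, which is 29%.
- Non-smokers: 4 + 14 + 24 + 28 = 70. Expected failures: 1.4 + 2.1 + 8.4 + 2.8 = 14.7, which is 21%.
- Pooled odds ratio: (0.29/0.71) / (0.21/0.79) = 1.54. Inside every group it is 1.00.

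**Dependence on the quotas.** Keep the same rates but use an illustrative mix of 10/20/40/70.
- Smokers: 9 + 6 + 16 + 21 = 52, with 3.15 + 0.9 + 5.6 + 2.1 = 11.75 failures (22.6%).
- Non-smokers: 1 + 14 + 24 + 49 = 88, with 0.35 + 2.1 + 8.4 + 4.9 = 15.75 failures (17.9%).
- Pooled odds ratio: (0.226/0.774) / (0.179/0.821) = 1.34.

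The patients within each group are unchanged. Only the quotas moved the figure from 1.54 to 1.34.

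**Rejection rates by simulation.** The pooled uncorrected Chi-square is compared with a Cochran-Mantel-Haenszel test stratified on the four groups. The true within-group association is zero.

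| Smokers (%) | Fail rates (%) | Pooled Chi-square rejects |
|---|---|---|
| 90/30/40/30 | 20/20/20/20 | 5% |
| 90/30/40/30 | 25/15/25/15 | 8% |
| 90/30/40/30 | 35/15/35/10 | 20% |
| 90/30/40/30 | 45/15/45/10 | 31% |
| 95/35/35/35 | 25/20/25/15 | 7% |
| 95/35/35/35 | 30/25/25/15 | 10% |
| 95/35/35/35 | 35/20/30/10 | 18% |
| 95/35/35/35 | 45/25/35/10 | 28% |

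The stratified test stays at 4-6% throughout. Oral corticosteroid use showed no inflation (4-6%), so the problem does not affect every characteristic.

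**FEV1.** Section 14.4 plans only box-plots here, so no rejection rate applies to the plan as written. As an illustration, assume mean FEV1 of 1.4/2.1/1.8/2.9 L with SD 0.55. In the last four fail-rate scenarios of the table, a pooled rank test would then reject in 14%, 21%, 52% and 77% of studies. The same shift would show in a pooled box-plot.

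**Age.** Stratifying on the four groups is the wrong remedy for age. At the 70-year cut, each asthma group lies wholly on one side, so 20 + 40 + 40 = 100 of the 140 patients contribute nothing to a stratified test. Assume a genuine age effect (35% failing at 70 or over, 15% below) and half of COPD patients aged 70 or over. Power then falls from about 79% pooled to about 30% stratified.

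**The case against.** The strongest case against runs as follows. The study is declared exploratory, and the protocol speaks of correlation and association throughout. An unadjusted association is a legitimate description. The sentence that asks for overall correlations also asks for them per subgroup, and those are free of differences between groups. Diagnosis is itself examined, and the groups are compared directly, so a reader would see pooled, within-group and between-group results together. The synopsis promises multiple regression. The simulated rates rest on inputs that no document supplies, and stratifying everything would destroy most of the information on age.

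Much of this stands. The distortion is conditional: with equal fail rates there is none. A reader might infer that the plan presents group differences as effects of patient characteristics, or that the overall results are bound to be spurious. The protocol supports neither reading. A reader might also conclude that every overall analysis should be replaced by a stratified one; the age calculation shows why that would be wrong.

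Three parts do not answer the point. The per-subgroup correlations rest on 20 to 40 patients each, and nothing in 14.4 combines that within-group information across the 140. The synopsis regression concerns a different outcome, names no covariates and is missing from 14.4. Finally, an exploratory association that depends on the chosen quotas can mislead as an association. Section 14.4 wants the groups to reflect their occurrence in society, and preset sizes do not secure that.

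**Conclusion.** The point holds in a limited form. Section 14.4 gives no group-stratified or group-adjusted analysis for the overall correlations that 7.2 requests, and the synopsis regression does not fill the gap. Where both the fail rate and the characteristic differ between groups, the pooled result can come entirely from group membership and the quota mix.

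Under the assumed inputs, the planned Chi-square for smoking rejects in about 5-30% of studies with no within-group association, against 4-6% when stratified. The lower end applies when fail rates are equal or nearly so. The upper end needs a large spread, for example 45% failing in COPD and 10% in mild-to-moderate asthma. All fail rates, smoking prevalences, FEV1 values and the 0.05 level are assumptions. What follows from the protocol alone is the structure: preset groups, defined by diagnosis, age and severity, pooled without adjustment.

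**What to change.** In section 14.4:

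- For sex, height, weight, FEV1, FVC, PIF, smoking status and oral corticosteroid dose, keep the unadjusted overall result and set beside it one that accounts for patient group. Use the Cochran-Mantel-Haenszel test with a common odds ratio for categorical variables, and a logistic model with patient group as a factor for continuous ones, with 95% confidence intervals. Base statements about characteristics across the whole sample on the adjusted result.
- Do not adjust age for the four groups, since age defines them. Analyse it adjusted for diagnosis and asthma severity, and report the contrast between the age-defined groups as a between-group contrast. The GINA step, already collected, could serve as the severity measure.
- Restrict GINA step to the asthma groups, and GOLD grade and group to COPD. Severity partly defines the asthma groups, so the pooled GINA result needs the same caution as age.
- Reconcile 14.4 with the synopsis regression: either carry it over with its outcomes and covariates listed, or remove it from the synopsis.

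This costs a few lines of text and a few more analyses, all on data already to be collected. The adjusted estimates use within-group variation only, so their intervals will be somewhat wider.

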7.3 Endpoints

Cfr 7.1 and 7.2

8 Investigational Plan

8.1 Overall Study Design

Cross sectional study design

8.2 Study Duration for Subjects

8.2.1 *Screening*

Patients will be recruited following their consultation with their pulmonologist. The recruitment of the patients will take place in the respiratory outpatient clinic of UZ Brussel.

8.2.2 *Treatment Period NA*

8.2.3 *Unscheduled Visit(s) NA*

8.2.4 *Early Study Termination NA*

8.2.5 *End of Study*

The duration of the study for each individual patient will be around 5 to 10 minutes. Participation ends when the patient leaves the pulmonology division at the outpatient clinic.

9 Selection of Subjects

9.1 Selection of Study Population

The selection of study population will take place in the respiratory outpatient clinic in UZ Brussel. The patients will be recruited following their consultation with the pulmonologist.

9.2 Inclusion Criteria

- COPD patients (GOLD II-IV)
- Patients with severe asthma included in the Belgian Severe Asthma registry aged <70
- Patients with asthma of any severity aged ≥ 70 y
- Patients with mild-to moderate asthma aged < 70y

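### Asthma is split by severity below 70 but pooled from 70 up, so the planned age comparison within asthma is confounded by an unstated severe share

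*Protocol*

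**What the plan says.** Section 9.2 defines three asthma groups by two factors, age and severity:

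- "Patients with severe asthma included in the Belgian Severe Asthma registry aged <70"
- "Patients with mild-to moderate asthma aged < 70y"
- "Patients with asthma of any severity aged ≥ 70 y"

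The synopsis (section 1) gives the sizes: "40 COPD patients (GOLD II-IV); 20 patients with severe asthma, 40 patients with asthma aged ≥ 70 y", followed by 40 mild-to-moderate asthma patients below 70. That makes 140 patients, 100 of them with asthma.

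Section 14.4 then fixes the analysis. "The comparison of the prevalence of patient/device mismatch between patient subgroups", and the same comparison for each test's fail rate, "will be done by means of the Chi-square test and will be visualized in cross-tables". For the link between characteristics and passing or failing each test, "box-plots will be used for continuous variables (for example weight and length), whereas the Chi-square test will be used for categorical variables"; age is one of the examples listed for the Chi-square.

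Section 7.2 makes mismatch per subgroup a secondary objective. It does the same for the correlation of fail rates with characteristics, including age and GINA treatment step, both per subgroup and overall. Section 6.1 lists age and GINA step among the data taken from the patient file. The synopsis also announces a multiple regression for inability to use each device class, which section 14.4 does not mention.

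**The concern.** Age and severity are not crossed. The group aged 70 and over has no younger group of like severity: unless it holds only one severity class, it is older and more severe on average than the mild-to-moderate group below 70, and older and milder than the severe group below 70. Below 70 the quotas set the severe share at 20/60, one third. From 70 up the share is whatever recruitment happens to give. It may also include severe patients outside the registry, who are not eligible below 70.

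Taking age alone across all asthma patients has the same defect, because severity differs between the age bands.

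Section 5.4 makes age relevant: "Poor inhaler use is most common in older ages, but can occur at all ages". A dedicated group of 40 aged 70 and over will naturally be read as the study's evidence on age. As section 14.4 stands, a severity effect could be reported as an age effect. A real age effect could also be masked in the comparison with the severe group.

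**Working it through.** The protocol gives no expected rates, alpha or power, so there is no figure to reproduce. The check asks whether the age effect can be recovered from the planned table, and how large the distortion could be.

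**Inputs from the protocol.** COPD 40; severe asthma below 70, 20; asthma 70 and over, 40; mild-to-moderate asthma below 70, 40.

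**Assumed.** All rates, the severe share *s* at 70 and over, and a 5% two-sided level.

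**Step 1: is the age effect identifiable?** Write the rate at 70 and over as

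p(≥70) = p(mild-to-moderate <70) + age effect + *s* × (p(severe) − p(mild-to-moderate)).

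Take 20% for mild-to-moderate, 40% for severe and 30% for COPD:

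| Age effect | *s* | Rate at ≥70 |
|---|---|---|
| 0 | 0.50 | 0.20 + 0 + 0.50 × 0.20 = 0.30 |
| +0.05 | 0.25 | 0.20 + 0.05 + 0.25 × 0.20 = 0.30 |
| +0.10 | 0 | 0.20 + 0.10 + 0 = 0.30 |
| −0.10 | 1 | 0.20 − 0.10 + 1 × 0.20 = 0.30 |

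All four cases give the same four-group table. The pooled rate is (12 + 8 + 12 + 8)/140 = 0.286. The noncentrality is Σ n(p − 0.286)² / (0.286 × 0.714) = 0.571/0.204 = 2.80 in every row. The test cannot tell a zero, positive or negative age effect apart, and more patients would not change that.

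**Step 2: how large could a spurious age difference be?** Set the age effect to zero and mild-to-moderate to 10%. The expected difference from the mild-to-moderate group below 70 is *s* × (severe rate − 10%). For a 40% severe rate it is 0.20 × 30 = 6 points at *s* = 0.20 and 0.50 × 30 = 15 points at *s* = 0.50. Simulated trials, with the number of severe patients among the 40 drawn binomially, gave these rejection rates:

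| Mild-to-moderate vs severe rate | ≥70 vs mild-to-moderate <70, uncorrected Chi-square, *s* = 0.20 to 0.50 | Same, Yates-corrected | Mantel-Haenszel age test stratified by severity |
|---|---|---|---|
| 10% vs 20% | about 7–11% | about 2–4% | about 5% |
| 10% vs 30% | about 9–25% | about 3–13% | about 5% |
| 10% vs 40% | about 14–44% | about 5–29% | about 5% |

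**Step 3: what would a stratified estimate deliver?** Use 20% and 40% again and an inverse-variance combination over the two severity strata. At *s* = 0.25 there are 10 severe and 30 mild-to-moderate patients aged 70 and over:

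- severe stratum variance: 0.4 × 0.6 × (1/20 + 1/10) = 0.0360
- mild-to-moderate stratum variance: 0.2 × 0.8 × (1/40 + 1/30) = 0.0093
- SE = √[1/(1/0.0360 + 1/0.0093)] = 0.086, so the 95% half-width is 1.96 × 0.086 = 17 points

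For *s* of 0.10, 0.50 and 0.75 the half-widths are 17, 18 and 20 points. The age effect becomes estimable, though not precisely.

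**The case against.** **No stated aim is defeated.** The study calls itself purely exploratory, its primary objective is overall mismatch prevalence, and no objective asks to isolate age from severity. This stands and limits the weight of the point. It does not remove it, since section 7.2 does ask for the relation of fail rates to age and to GINA step, and section 14.4 answers one variable at a time.

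**Other planned analyses help.** The synopsis regression could adjust for severity, and correlations within subgroups look at age inside each younger group. This stands in part. The regression has a different outcome (inability to use a device class), lists no covariates and is absent from section 14.4. Correlations of age inside a younger group do not compare patients below 70 with those above it.

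**This is SAP matter.** Adjusted analyses are often left to a SAP, and none is shown. The protocol nevertheless fixes both the grouping and the test itself. The data for a better analysis are collected, so nothing is lost beyond repair.

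**The size rests on assumptions.** This stands. The 14–44% range needs a fourfold severity effect and an uncorrected pairwise test, which section 14.4 does not spell out. With Yates correction the smallest scenario does not exceed 5%.

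Two stronger readings are not supported. A reader might infer that the design allows no severity contrast at all; severe against mild-to-moderate below 70 is such a contrast within one age band. A reader might also infer that stratifying gains power. With a true 20-point age effect on 15%, no severity effect and a COPD rate of 20%, the four-group test has about 48% power and the stratified test about 64%. A crude test of 70 and over against below 70 gives 65%, so the gain comes from using one degree of freedom instead of three.

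**Conclusion.** The point holds for the age comparison within asthma only. Neither the row for patients aged 70 and over nor age taken alone can be read as an age effect, because the severe share in that group is not set. Overall mismatch prevalence and the severity contrast below 70 are sound.

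The identifiability argument needs no assumed rates. The size does: the distortion is slight if severity matters little or few of the older patients are severe, and substantial if severe patients fail several times as often and make up a large part of the group. Since it concerns a secondary, exploratory comparison, section 14.4 should be changed, but the study's main result does not depend on it.

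**What to change.** In section 14.4, keep the four-group table and add the following:

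1. Classify severity in all 100 asthma patients by one stated rule, for example the GINA treatment step already collected. Using registry membership below 70 and GINA step above would leave strata that are not alike.
2. Report mismatch and each fail rate by age band and severity within asthma. Add an age contrast (70 and over against below 70) stratified by severity, by Mantel-Haenszel, with a risk difference and 95% CI. Alternatively, carry the synopsis regression into section 14.4 with age and severity as covariates, for mismatch and for each fail rate.
3. State that the raw row for patients aged 70 and over is not an age effect.

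The cost is a few sentences and no extra patients. If GINA step is the rule, no new measurement is needed. The drawback is imprecision: a 95% half-width of roughly 17–20 points under the rates assumed above, and possibly few severe patients aged 70 and over.
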